- 1. Recruitment feasibility:** Recruiting 32 participants is challenging for a 2-year pilot study. The primary recruitment site will be the VAMC. Established relationships with 3 other regional hospitals will be used to expand recruitment, with a future protocol amendment as needed. In addition, recruiting Veterans with either transfemoral or transtibial LLA provides a larger recruitment pool than limiting the LLA to one specific level.
- 2. Functionality of the mobile-health technology:** Durability and continued functionality is a concern when using any technology. The mobile-health tablets used in this study are used in standard of care for a variety of purposes in the VA Eastern Colorado Health Care system. If a tablet becomes dysfunctional, replacement units are available for immediate replacement. The VA will provide mobile-health technical support for the duration of the study (See letter of support from [name]). Finally, the PABC intervention is not dependent on equipment brand, so future changes in equipment will not necessitate change in intervention.
- 3. Long-term behavior change:** Creating lasting change in physical activity behavior is a major challenge. We will collect data out to 6 months (GROUP1) to determine persistence of intervention effects. We expect activity changes may be reduced at the 6-Month time period compared to the 3-Month test point, but expect activity to remain higher than baseline, based on data from studies of patients with other chronic diseases.²
- 4. Transtibial and transfemoral LLA:** Response to intervention may differ between Veterans with transfemoral and transtibial LLA. We have included both levels of amputation, as both are linked to low activity and high disability. We will protect against such differences by stratifying randomization by level of amputation.

E. Study Timeline and Enrollment Goals:

TASK	Year 1				Total (1)	Year 2				Total (2)	TOTAL
Personnel Training											
Screening											
Enrollment (n=32)	4	4	6	6	20	6	6			12	32
Data Collection, Processing & Analysis											
Abstracts/Manuscripts											

F. Future Investigation:

This pilot project is an important stepping-stone for a larger research line focused on optimizing physical activity and minimizing disability for Veterans with dysvascular LLA. Data from this pilot study will inform a larger intervention trial targeting mobile-health physical activity change (future VA Merit Review proposal).

REFERENCES

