We will recruit older Veterans with dysvascular LLA (1-5 years after LLA) to participate in the PABC intervention, which uses established VA Health Care system technology and evidence-based intervention methods. The five key dimensions of feasibility to be assessed are whether Veterans: 1) can successfully participate in the intervention (practicality), 2) tolerate physical activity progression (implementation feasibility), 3) are interested and enjoy the intervention (acceptability), 4) complete the intervention safely (safety), and 5) respond to the intervention with increased activity and decreased disability (responsiveness).^{31,32} Measures of physical activity and disability will be used to establish effect size estimates for the PABC intervention, with the intention of planning a future clinical efficacy trial. Testing will occur at baseline (pre-intervention), three months (end of intervention), and six months, using a two-group randomized crossover design.

Primary Aim: Determine feasibility of using the PABC intervention with older Veterans who have dysvascular LLA by assessing: 1) practicality (measured by retention rate), 2) implementation feasibility (measured by dose goal attainment), 3) participant acceptability (measured by the Intrinsic Motivation Inventory (IMI) – Interest / Enjoyment Subscale), and 4) safety (measured with Adverse and Serious Adverse Events).

Hypothesis 1.1: Retention rate will be at least 85% over the PABC intervention period (i.e., ≤15% attrition).

Hypothesis 1.2: At least 75% of participants will meet the dose goal of a 3% average increase in daily steps per week, across the three months of intervention.

Hypothesis 1.3: Participants will indicate PABC intervention acceptability with a mean score of ≥ 5/7 on the IMI – Interest / Enjoyment Subscale.

Hypothesis 1.4: There will be similar rates of study related (definitely, probably, possibly) adverse events between groups during the first three months (period of direct comparison of intervention versus control).

Secondary Aim: Establish effect size estimates of the PABC intervention (responsiveness)

using physical activity and self-report disability outcomes.

Hypothesis 2.1: The PABC group will have increased activity counts and less self-reported disability than the control group at Month 3, each with effect size estimates ≥ 0.80 (Cohen's d).

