The FitBit sensor will be used to guide the intervention and data from the sensors will NOT include personal health information; with generic accounts will be created for each user without participant-identifiable information. FitBit data will not be used as outcomes, but rather, only to guide the PABC intervention. Outcome data will be managed using the REDCap (Research Electronic Data Capture) platform. REDCap is a secure, web-based application designed to support research data capture, providing user-friendly case report forms, real-time data entry validation (e.g., data type and range checks), audit trails, transaction logs, and a de-identified data export to common statistical packages. The VA Eastern Colorado Health Care System has approved REDCap for research use. More detail is provided in the Human Subjects section.

D.8. Sample Size Estimate

The sample size estimate was based on evidence for activity change in patients with DM and PAD, which indicates a reasonable expected increase of 3% walking activity per week (e.g., steps, distance, time) over 3 months.^{3, 12, 77, 78} A baseline mean (SD) of 2000 (900) steps/day was estimated based on data from our ongoing dysvascular LLA RCT (Section C.3.) and published LLA data.^{49, 79, 80} A 3% weekly increase in steps during intervention, assuming no order effect, would provide an effect size of 0.8 (Cohen's d). Based on those assumptions, a sample size of 13 per group with a crossover design (total n=26) provides >95% power to detect an intervention effect (effect size=0.8, $\alpha=0.05$, two-tailed paired t test). The study is generously powered intentionally, because the assumption of 'no order effect' will not likely hold. We will recruit 32 participants, and expect at least 26 to complete. This 15% attrition estimate is conservative, based on an historical attrition rate <15% in our intervention studies with other older adult populations^{81, 82} and our current dysvascular LLA RCT.

D.9. Data Analysis Plan

Aim 1 (Feasibility of PABC Intervention): The analyses for Aim 1 are based on four hypotheses: H1.1) participant retention, H1.2) dose goal attainment, H1.3) intervention acceptability, and H1.4) safety.

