Determining feasibility of the PABC intervention will set the stage for implementing a larger efficacy study. The expected result is that Veterans with LLA can be enrolled and retained in the PABC intervention with adherence to a 3% weekly increase in physical activity dose. In addition, the effect size is expected to be ≥ 0.80 . While similar interventions have been feasible and successful for other chronic disease populations, this trial will be the first to target chronic physical inactivity behavior for Veterans living with dysvascular LLA.

D.11. Participant Safety

Anticipated adverse events include falls and medical complications due to DM and PAD. A Safety Officer ([name]) for the study will meet with the PI quarterly to review study progress and adverse events. [name] is the Outpatient Medical Director for Rehabilitation Services at the Denver VAMC. [name] is also an Associate Professor in the Department of Physical Medicine and Rehabilitation at the University of Colorado. Beyond his clinical expertise, [name] has experience in outcomes research related to patients with LLA and functional exercise interventions. Fall risk will be monitored using the TUG test and Falls Efficacy Scale-International (FES-I) at all test points (baseline, 3M, 6M). Also, occurrence of falls will be recorded at each of weekly visit in both the intervention and control periods. Fall occurrences and other adverse events will be reported on a quarterly basis to the Safety Officer. The incidence of falls, defined as “inadvertently coming to rest on the ground, floor or other lower level, excluding intentional change in position”,⁸⁴ will be of particular focus. All study-related falls (possibly, probably, or definitely) will be tracked. If the total number of falls reaches 4, the Safety Officer will review incidence by group. If the number of falls for the intervention group exceeds that of the control group by 3 (10% of enrollment) at any time, the study will be suspended until an evaluation of study relatedness for each incidence is performed by the Safety Officer.

D.12 Potential Pitfalls and Alternative Strategies

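### Hypothesis 2.1 sets its mark for the observed effect (d of at least 0.80 on both outcomes) at the effect assumed in planning, so an intervention with exactly that true effect would miss it about 49% to 75% of the time

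*Combined protocol and SAP*

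**What the plan says.** Hypothesis 2.1, under the Secondary Aim in section A, compares the PABC group with control on activity counts and self-reported disability and expects better results "than the control group at Month 3, each with effect size estimates ≥ 0.80 (Cohen's d". The mark is set on the estimates, and it applies to each of the two outcomes.

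Section D.8 uses the same number as the assumed true effect. It starts from steps: "A baseline mean (SD) of 2000 (900) steps/day was estimated". It then states: "A 3% weekly increase in steps during intervention, assuming no order effect, would provide an effect size of 0.8 (Cohen's d". On that basis "a sample size of 13 per group with a crossover design (total n=26) provides >95% power to detect an intervention effect", using a two-tailed paired t test at alpha 0.05. D.8 assumes no effect for LLFDI and gives no correlation between the two outcomes.

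Section D.9 computes Cohen's d from the mean and SD of change in activity counts and LLFDI, and bases inference on linear models. It specifies no confidence interval for d and no decision rule for Aim 2. Section D.10 repeats the mark as a forecast: "In addition, the effect size is expected to be ≥ 0.80". Hypothesis 2.2, under the same aim, asks only that means and SDs be obtained for sizing a later trial.

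**The concern.** Power to reject zero and the chance that an estimate reaches a given value are different quantities. D.8 addresses the first and Hypothesis 2.1 is worded as the second. When the mark equals the true effect, the chance of reaching it stays close to one half per outcome whatever the sample size, and requiring both outcomes lowers it further. More participants do not help.

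At stake is how the responsiveness result is reported. Read literally, Hypothesis 2.1 could be declared not met for an intervention that performs exactly as planned, because of sampling variation around 0.80. The intended use of Aim 2 is to inform a larger trial, and for that the estimate and its precision matter more than the side of 0.80 on which it falls.

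**Working it through.** **Inputs from the plan.** Baseline 2000 (SD 900) steps/day, 3% weekly increase over 3 months (taken as 12 weeks), paired t test, two-sided alpha 0.05, 26 completers (13 per group) or 32 recruited (16 per group): all D.8. Mark of 0.80 on each of two outcomes at Month 3: Hypothesis 2.1. SD of change as the scale for d: D.9.

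**Assumptions added here.** Normal outcomes, equal SDs, equal groups, unadjusted d, both outcomes scored so that improvement is positive, and a between-outcome correlation r from 0 to 1. A true d of 0.80 for LLFDI is also added, since D.8 covers steps only.

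**1. The plan's own figures.**
- Effect size: 12 × 0.03 × 2000 / 900 = 720 / 900 = 0.80. This reproduces with a linear increase.
- Power: noncentral t with df = 25 and noncentrality 0.8 × √26 gives 97.5%. The stated >95% is correct for that test.

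**2. Chance that one observed d reaches 0.80 when the true d is 0.80.** With n per group, the observed d is at least 0.80 when t ≥ 0.8 × √(n/2). Here t is noncentral with df = 2n − 2 and noncentrality also 0.8 × √(n/2).
- 13 per group: 0.508
- 16 per group: 0.507
- Paired d with n = 26, if the crossover comparison is used instead: 0.515

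**3. Chance that both reach 0.80 when the true d is 0.80 on both.** The large-sample formula is 1/4 + arcsin(r)/(2π), which gives 0.25 at r = 0, 0.33 at r = 0.5 and 0.50 at r = 1. Simulation at the trial's sizes (200,000 trials per setting) gives:

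| r | 13 per group | 16 per group |
|---|---|---|
| 0 | 0.258 | 0.258 |
| 0.3 | 0.303 | 0.304 |
| 0.5 | 0.339 | 0.337 |
| 0.7 | 0.379 | 0.378 |
| 0.9 | 0.435 | 0.432 |

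At r = 1 the two outcomes act as one, and the chance is the single-outcome 0.51. The range is about 25% to 51% met, so about 49% to 75% not met.

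**4. Sensitivity to the scale of d.** D.8 divides by the baseline SD, while D.9 uses the SD of change. With equal SDs at both times and pre-post correlation ρ, the SD of change is the baseline SD × √(2(1 − ρ)). The two scales agree only at ρ = 0.5. At ρ = 0.7 (assumed), d = 0.80 / √0.6 = 1.03. One observed d then reaches 0.80 with probability 0.72 (13 per group) or 0.74 (16 per group). Both do so in about 52% to 68% of trials for r = 0 to 0.9.

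**5. Sensitivity to LLFDI.** If the true LLFDI d were 0.5 (assumed), with 0.80 for activity and 16 per group, both reach 0.80 in 11% to 16% of trials for r = 0 to 0.5.

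**6. Precision of an observed d of 0.80.** The approximate SE is √(2/n + d²/(4n)).
- 13 per group: √(0.1538 + 0.0123) = 0.408, so the 95% CI is 0.00 to 1.60.
- 16 per group: √(0.1250 + 0.0100) = 0.367, so the 95% CI is 0.08 to 1.52.

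**The case against.** The strongest reply is that no pass/fail rule exists here. D.9 names results that count as negative for dose attainment and acceptability but none for Aim 2, and it assigns inference to linear models. D.10 words 0.80 as an expectation, the aim is one of estimation, and no later step depends on 0.80. Hypothesis 2.2 is a second hypothesis under the same aim and can be satisfied whatever d turns out to be. All of this stands, and it limits the point to how Hypothesis 2.1 is concluded. It does not remove it: with no rule or interval in D.9, the literal 0.80 is the only stated mark for responsiveness.

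It is also fair that 0.80 on the baseline SD is not 0.80 on the change SD. With a pre-post correlation above 0.5, meeting Hypothesis 2.1 can become more likely than not, as step 4 shows.

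Two stronger readings are tempting and are not supported. A reader might infer from D.8 that the risk of missing Hypothesis 2.1 is below 5%. D.8 does not say so: it ties >95% to detecting an effect with a paired test and mentions neither the 0.80 mark nor LLFDI. A reader might also fix the failure rate at two in three. That needs a between-outcome correlation near 0.5, which the plan does not give.

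**Conclusion.** The point holds as a matter of how Hypothesis 2.1 is worded and concluded. At a true d of exactly 0.80 on both outcomes, the literal criterion is missed about 49% to 75% of the time, and where in that range depends on the unstated between-outcome correlation. The result rests on the added LLFDI assumption and on taking 0.80 as the true value on D.9's scale. A larger true d on the change scale improves the odds to about 52% to 68% met in the example at 1.03, and a smaller LLFDI effect worsens them. The power figure in D.8 is not in error; it answers a different question. The primary feasibility aim and Hypothesis 2.2 are unaffected.

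**What to change.** - **Hypothesis 2.1 and D.10:** state the hypothesis as direction, that is, higher activity counts and less self-reported disability than control at Month 3, and label 0.80 as the planning value.
- **D.9:** report each d with its 95% CI, and draw the Hypothesis 2.1 conclusion from the interval (its direction, and whether it includes 0 and 0.80), not from whether the point estimate reaches 0.80.
- **D.8:** add that >95% refers to rejecting zero effect on a single activity outcome, and that it covers neither the 0.80 mark, the two-outcome requirement nor LLFDI.

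The cost is wording in four places and two confidence intervals, with no added participants, visits or data. The downside is that Hypothesis 2.1 no longer claims a large effect as its mark, and the power statement reads less favourably. The change should be made before results are seen.

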The proposed pilot study is a randomized, tester-blinded design assessing PABC intervention feasibility (Aim 1) and effect size (Aim 2). Randomization ($n=32$) will create two groups (GROUP1 or GROUP2) using computer-generated random blocks of 2 and 4, stratified by amputation level (transtibial and transfemoral). An investigator not involved with testing or intervention ([name]) will conceal group allocation. A crossover design is used to simultaneously accomplish the aims and optimize recruitment (Fig.2). The PABC Intervention will be delivered to both groups (GROUP1 during Months 1-3 and GROUP2 during Months 4-6). The crossover design provides $n=32$ for assessing Aims 1 and 2. Intervention effect retention will be tested at six months for GROUP1 ($n=16$).

D.1. Setting

The study will occur at the VA Geriatric Research Education and Clinical Center (GRECC), where Drs. [name] and [name] have dedicated positions ([name] (GRECC Director)). Intervention delivery will occur with the participant at home and therapist at a VA site with access to tablet interface software (e.g. VA Jewell Motion Analysis Lab or VA Clinical Building South, using VA-supplied and approved mobile-health tablets and wearable activity sensors (FitBit)).

D.2. Participants

Thirty-two participants will be recruited from the Denver VAMC. The target sample is older Veterans diagnosed with PAD and/or DM, who have major LLA. We expect $<15\%$ attrition, with a goal of 26 participants completing.

D.3. Eligibility Criteria

Inclusion criteria: ≥ 50 years of age, LLA 1-5 years prior, Type II DM and/or PAD, and

ambulatory without human assistance, in the home or better using a prosthesis, with assistive device as needed, with assistive device as needed. Exclusion criteria: wheelchair as primary form of locomotion, trauma or cancer-related etiology of the LLA, unstable heart condition, uncontrolled hypertension, acute systemic infection, cancer, recent stroke (within 2 years), or lower extremity wound or ulcer that limits ambulation.

D.4. Recruitment Strategies

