All participants will be recruited from the Denver VA Medical Center (VAMC) or Veterans that are receiving care outside of the VA system in our core-group of regional hospitals. [name] and [name] will use the Amputation Clinic database and meet with the rehabilitation teams to obtain names of Veterans meeting the inclusion criteria. A research team member will then contact the potential participant in person or by letter and ask for permission to explain and complete a brief screening form to determine the Veteran's eligibility. We will increase the recruitment pool for this study from our previous studies, by allowing participants with both transfemoral and transtibial amputation. Recruitment from the Denver VAMC is expected to be feasible based on Denver VAMC data (47 new Veterans seen in rehabilitation for new major LLA in last 18 months).

D.5. Intervention

The home-based study design is intended to reduce participant burden by removing transportation and time barriers. There will be two participation periods of three months (Months 1-3 and 4-6). PABC intervention will occur Months 1-3 for GROUP1 and Months 4-6 for GROUP2 (Fig.1). GROUP2 will participate in a no-exercise, attention control in Months 1-3. GROUP1 will have a no contact, intervention "wash-out" period in Months 4-6.

Study Initiation. A physical therapist will initially meet with the participant at the participant's home to: 1) obtain informed consent and authorization, 2) deliver and orient the participant to wearing an activity monitor (ActiGraph Inc. Pensacola FL), and 3) assess the prosthetic fit and function (Prosthetic Evaluation Questionnaire). If prosthetic fit and function concerns are identified, the participant will be given recommendations for seeing his/her prosthetist, which must be met before beginning the intervention. The participant will wear the ActiGraph monitor for 10 days after the initial visit. The ActiGraph monitor will be used only for outcome data (not intervention) and provides no feedback to participants.

Following the initial visit, participants will be randomized (GROUP1 and GROUP2).

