Each week will include scripted education delivered by the therapist during the video interaction, on a relevant intervention topic (e.g., fall prevention, monitoring blood sugar and diet relative to increasing activity, etc.) (10 minutes). The initial education topic will be fall prevention, to minimize fall risk during the study period.

No-Exercise Attention Control Period. During Months 1-3, GROUP2 will weekly have weekly video interactions with a therapist using the mobile-health tablets, in a no-exercise control period. These meetings will provide health and safety education on non-exercise topics pertaining to older Veterans (e.g., fall prevention, diet, medication management, retirement issues, etc.). Physical activity recommendations will not be discussed. Each week will include scripted education on one topic (10 minutes) and a brief period of light upper and lower extremity range of motion tasks led by the therapist with the video interface and participants seated in a chair (20 minutes). As in the PABC intervention period, the initial education topic for the Control period will be fall prevention, to minimize fall risk during the study period. The rationale for the no-exercise control period is to determine the natural change in physical activity and disability without PABC intervention, while accounting for any potential benefit from contact with the physical therapist (i.e., attention control).

D.6. Outcomes

Outcomes will be measured during in-home visits (Baseline, 3M, and 6M), instead of remotely, to promote safety and reduce fall risk during the test session. Aim 1 outcomes will be 1) participant retention rate, 2) dose goal attainment, 3) acceptability (Intrinsic Motivation Inventory – Interest/Enjoyment Subscale¹⁰), and Adverse & Serious Adverse Events). Aim 2 outcomes, to assess effect size, will be average 10-day physical activity counts (ActiGraph monitors^{2, 11}) and self-report disability (Late-Life Function and Disability Index (LLFDI)^{12, 13}). In addition, Baseline descriptive measures include demographics, medications, cognition (Folstein Mini-Mental State Exam¹⁴), depression (Geriatric Depression Scale SF^{15, 16}), residual limb quality (Chakrabarty Scale¹⁷), sensory testing (Michigan Neuropathy Screen^{18, 19}), exercise readiness to change (Exercise Stages of Change^{20, 21}), prosthesis description, and comorbidities (Functional Comorbidity Assessment²²).

D.7. Data Management

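### The crossover does not provide n=32, nor D.8's paired power, for Aim 2's PABC-versus-control effect, which rests on 16 versus 16 at Month 3

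*Combined protocol and SAP*

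**What the plan says.** Section D describes a two-group crossover with 32 randomised. GROUP1 receives PABC in Months 1-3 and GROUP2 in Months 4-6. It then says: "The crossover design provides $n=32$ for assessing Aims 1 and 2". The same paragraph assigns the six-month data of GROUP1 (n=16) to testing whether the effect is retained.

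The other period of each group is not the same condition:

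- GROUP2 has weekly therapist video contact without exercise in Months 1-3. D.5 gives the purpose as "to determine the natural change in physical activity and disability without PABC intervention, while accounting for any potential benefit from contact" with the therapist.
- For Months 4-6, D.5 says "GROUP1 will have a no contact, intervention" wash-out period.

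D.12, item 3, says that six-month activity may fall below the Month 3 level, "but expect activity to remain higher than baseline, based on data from studies of patients with other chronic diseases".

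Hypothesis 2.1 (section A) compares the PABC group with the control group at Month 3. D.9 computes Cohen's d from the mean and SD of change and fits linear models with diagnosis, group and baseline value. It names no time point for either, and the models have no period, sequence or participant term.

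D.8 reports more than 95% power for 26 completers (13 per group) in a crossover, with d = 0.8 and a two-tailed paired t test at 0.05. It adds that the study is generously powered "because the assumption of 'no order effect' will not likely hold".

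**The concern.** A crossover gains its efficiency when each participant is observed under both conditions, so that each serves as their own control. That is what a paired test on all 26 completers would need if it is to estimate PABC against control. Only GROUP2 is observed under both attention control and PABC. GROUP1 goes straight from PABC into a period with no contact, no later treatment, and an effect that the protocol hopes will last. A wash-out normally separates two treatments; here the term is applied to a final follow-up period.

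The stated n and power for Aim 2 therefore do not describe the contrast that Aim 2 hypothesises. This matters because Aim 2 exists to supply an effect size for planning a larger trial. A reader who takes n=32 and more than 95% power at face value will expect a much more precise controlled estimate than the design gives. The answer to the doubtful order-effect assumption, generous power, does not help either: a larger sample does not remove carry-over, and the power figure belongs to a different comparison.

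**Working it through.** **Inputs.** From D.8: baseline 2000 steps/day, SD 900, 3% rise per week, d = 0.8, two-sided alpha 0.05, 13 per group completing (26 in total). From section D: 32 randomised, 16 in GROUP1. From section A: Month 3 contrast between groups. Assumed, because the documents do not give them: the baseline-to-Month-3 correlation r and the fraction f of the effect retained at six months.

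**1. D.8's effect size.** With linear growth over 12 weeks, 2000 × 0.03 × 12 = 720 steps, and 720/900 = 0.80. This matches. Compounding would give 2000 × (1.03^12 − 1)/900 = 0.95.

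**2. D.8's power.** For a paired t test with n = 26, the noncentrality is 0.8 × √26 = 4.08 with 25 df. Power is 97.5%, which agrees with the stated figure of more than 95%. The 0.8 is scaled by the between-person SD. Using it as a paired effect size implies a within-person correlation of 0.5, since 0.8/√(2(1 − 0.5)) = 0.8.

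**3. The Month 3 contrast.** For a two-sample t test with n per group, the noncentrality is 0.8 × √(n/2) with 2n − 2 df.

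| Per group | Noncentrality | Power, unadjusted | Approximate 95% CI if observed d = 0.8 |
|---|---|---|---|
| 13 | 2.04 | 49.9% | 0.00 to 1.60 |
| 16 | 2.26 | 59.1% | 0.08 to 1.52 |

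The intervals use SE = √(2/n + 0.8²/(4n)). By the same method, 80% power needs 26 per group and 95% needs 42.

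**4. With baseline adjustment, as D.9 plans.** The effective d is 0.8/√(1 − r²), with 3 df removed for covariates.

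| Assumed r | Power, 13 per group | Power, 16 per group |
|---|---|---|
| 0.3 | 53% | 63% |
| 0.5 | 61% | 71% |
| 0.7 | 78% | 86% |
| 0.8 | 90% | 95% |

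**5. If GROUP1's Months 4-6 were used as its control.** This is conditional: the documents do not specify it. On a level contrast (Month 3 minus Month 6), GROUP1 shows 0.80 × (1 − f). Averaged equally with an unbiased GROUP2, the pooled d is 0.80 × (1 − f/2).

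| Assumed f | GROUP1 d | Pooled d | Paired power, n = 26 |
|---|---|---|---|
| 0 | 0.80 | 0.80 | 97.5% |
| 0.5 | 0.40 | 0.60 | 83.6% |
| 1 | 0 | 0.40 | 50.0% |

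The better the effect lasts, the smaller it would appear.

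**The case against.** The strongest reply is that the plan never calls GROUP1's Months 4-6 a control. The only control it defines is GROUP2's attention period. Hypothesis 1.4 describes the first three months as the period of direct comparison, Hypothesis 2.1 is set at Month 3, and the D.9 model has the form of a parallel-group analysis. Section D and D.12 already use GROUP1's six-month data for retention. All of this stands, and it means that much of the remedy is already in the plan.

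The n=32 sentence also has innocent readings. Both groups receive PABC, so 32 pre-to-post changes are available (GROUP1 baseline to Month 3, GROUP2 Month 3 to Month 6). They can serve the means and SDs of Hypothesis 2.2. D.8's effect size is built as a gain from baseline, so its paired test may be a pre-post test. And all 32 do enter the Month 3 comparison. These readings are fair, but none rescues the claim for Hypothesis 2.1. Pre-to-post change is uncontrolled for PABC against attention control, and the Month 3 comparison gets its 16 versus 16 from randomisation, not from the crossover.

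A reader might infer that the planned Aim 2 estimate is biased by carry-over. The documents do not support that: no pooled period contrast is specified, and the retained fraction in step 5 is assumed. Nor is it right that GROUP1 has no untreated data, since it has a 10-day baseline recording. What it lacks is any attention-control period.

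**Conclusion.** The concern holds as a mismatch between the stated size and design basis of Aim 2 and the contrast that Aim 2 defines. The controlled effect is 16 versus 16 at Month 3, about 13 versus 13 if completers split evenly, and the crossover adds nothing to it. D.8's paired figure reproduces (97.5%) but does not carry over to that contrast, where unadjusted power at d = 0.8 is about 50% to 59%. Adjustment for baseline could bring it to between 53% and 95% over the assumed correlations of 0.3 to 0.8. These figures take D.8's d of 0.8, derived in steps, as the effect for Aim 2.

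It does not hold as a finding that a planned estimate is biased. The fall in pooled d to 0.60 or 0.40 would arise only if Months 4-6 were used as control on a level contrast, with 50% or 100% retention. The plan does not say it will do this. D.9 leaves room for it only by naming no time point. The n=32 claim remains sound for the Aim 1 outcomes measured during PABC.

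**What to change.** - In section D, limit the crossover n=32 claim to the Aim 1 outcomes measured during PABC and to uncontrolled pre-to-post means and SDs.
- In D and D.9, state that the Aim 2 effect size and linear models use the randomised Month 3 comparison, 16 versus 16. Treat GROUP2's change from Month 3 to Month 6 as supportive, and use GROUP1's six-month data for retention only.
- In the synopsis and D.5, rename GROUP1's Months 4-6 as no-contact follow-up.
- In D.8, say what the paired n=26 figure applies to, and give power or expected precision for the Month 3 contrast, with the assumed baseline correlation stated.

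The cost is mostly wording, plus a fresh power or precision statement in D.8. The downside is that the stated n and power for Aim 2 become less favourable. Visits, procedures and participant numbers do not change.
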